# 10.5 Interim Analysis and Early Stopping Guidelines

Since the study is open labeled no interim analysis will be performed to inform early stopping guidelines.

# **10.6** Planned Methods of Analysis

Summary tabulations will be provided for disposition, demographic, baseline, efficacy, and safety data as noted in the following sections.

All eCRF data, lab data, and any outcomes derived from the data will be provided in the patient data listings. Patient data listings will be presented for all patients enrolled into the study. Descriptive summary statistics including n, mean, median, standard deviation, standard error, interquartile range (25th percentile, 75th percentile), and range (minimum, maximum) for continuous variables, and counts and percentages for categorical variables will be used to summarize most data.

# 10.6.1 Demographic and Baseline Characteristics

Demographic and Baseline characteristics will be summarized using descriptive statistics by treatment group. All patients enrolled will be included in a summary of patient disposition.

# 10.6.2 Safety Analysis

Treatment duration and amount of Study Drug received will be summarized by treatment group and overall.

Injection Site Reactions (ISRs) will be summarized by treatment group, MedDRA preferred term and severity.

# 10.6.2.1 Adverse Events

Treatment duration and amount of Study Drug received will be summarized. Patient incidence rates of all AEs will be tabulated by MedDRA system organ class, and by MedDRA preferred term. Narratives of treatment-emergent deaths, serious and significant AEs, including early withdrawals due to AEs, will also be provided.

All treatment-emergent AEs, all treatment-emergent AEs potentially related to Study Drug, all treatment-emergent serious AEs potentially related to Study Drug will be summarized.

# 10.6.2.2 Clinical Laboratory Data

Laboratory tests to ensure patient safety including chemistry panel, complete blood count (CBC) with differential, coagulation panel, complement, etc., will be summarized by study visit. These safety variables will also be presented as change and percent change from Baseline over time after Study Drug administration, as appropriate. In addition, the number of subjects who experience abnormalities in clinical laboratory evaluations will be listed.

#### 10.6.2.3 Vital Signs and Examinations

Vital signs, weight, and ECG measures will be summarized by study visit.

#### 10.6.3 Efficacy Analysis

Change at week 27 relative to Baseline will be summarized for:

- Fasting TG
- MTT (plasma glucose, serum insulin, serum C-peptide, FFA, serum ghrelin, GIP, GLP-1 and PYY)
- Glycosylated hemoglobin
- HOMA-IR
- 24-hr glucose
- Adiponectin and leptin
- HFF
- Fat distribution

#### 10.6.4 Pharmacokinetic Analysis

The plasma PK of ISIS 703802 (as total full length oligonucleotides, including, fully conjugated, partially conjugated, and unconjugated ISIS 703802) will be assessed following multiple-dose SC administration. The plasma trough levels of ISIS 703802 during treatment period and those during post-treatment follow up period will be descriptively summarized with stratification by subject immunogenicity status if applicable.

Immunogenicity (IM) results (screen positive/negative, confirmed positive/negative or not evaluable, and when applicable, titer of anti- ISIS 703802 antibodies) before, during, and after treatment with ISIS 703802 will be listed. Subject ADA status (positive/negative or not evaluable) for all evaluable patients, along with the study day associated with the first positive IM status emerged ( $T_{first}$ , i.e., onset of ADA development), the last positive IM status observed ( $T_{last}$ ), the last ADA sample collection day, and subject - peak titer if applicable, will be listed and study day.

Additionally, the sample and subject IM incidence (number) and incidence rate (percent) will be summarized as the total number and percent of evaluated subjects with antibody negative, positive, and unknown status by treatment group. Furthermore, onset and titer of the ADA response, if applicable, will be summarized as median, quartiles (25% and 75%), and range.

# 10.6.5 Pharmacodynamic Analysis

The following parameters will be measured throughout the trial and change at week 27 relative to Baseline will be summarized:

- ANGPTL3
- HDL-C
- LDL-C
- TC
- VLDL-C
- non-HDL-C
- apoB
- apoB-48
- apoB-100
- apoA-1
- apoC-III
- Lp(a)
- FFA
- Glycerol levels
- Lipoprotein particle size/number

#### 10.6.6 Additional Analyses

Additional analyses may be performed not specified in this open label study protocol from the data available.

#### 11. INVESTIGATOR'S REGULATORY OBLIGATIONS

#### 11.1 Informed Consent

The written informed consent document should be prepared in the language(s) of the potential patient population, based on an English version provided by the Sponsor or designee.

Before a subject's participation in the trial, the Investigator is responsible for obtaining written informed consent from the subject or legally acceptable representative after adequate explanation of the aims, methods, anticipated benefits, and potential hazards of the study and before any protocol-specific screening procedures or any Study Drug ISIS 703802 are administered. The subject or legally acceptable representative must be given sufficient time to consider whether to participate in the study.

The acquisition of informed consent and the subject's agreement or refusal to notify his/her primary care physician should be documented in the subject's medical records and the informed consent form should be signed and personally dated by the subject or a legally acceptable representative and by the person who conducted the informed consent discussion (not necessarily an Investigator). The original signed informed consent form should be retained in the Study Master File and in any other locations required by institutional policy, and a copy of the signed consent form should be provided to the subject or legally acceptable representative.

If a potential subject is illiterate or visually impaired and does not have a legally acceptable representative, the Investigator must provide an impartial witness to read the informed consent form to the subject and must allow for questions. Thereafter, both the subject or legally acceptable representative and

the witness must sign the informed consent form to attest that informed consent was freely given and understood.

## **11.2** Ethical Conduct of the Study

The Guidelines of the World Medical Association (WMA) Declaration of Helsinki dated October 2002 the applicable regulations and guidelines of current Good Clinical Practice (GCP) as well as the demands of national drug and data protection laws and other applicable regulatory requirements will be strictly followed.

#### 11.3 Independent Ethics Committee/Institutional Review Board

A copy of the protocol, proposed informed consent form, other written subject information, and any proposed advertising material must be submitted to the IEC/IRB for written approval. A copy of the written approval of the protocol and informed consent form must be received by the Sponsor or designee before recruitment of subjects into the study and shipment of Study Drug. A copy of the written approval of any other items/materials that must be approved by the Study Center or IEC/IRB must also be received by the Sponsor or designee before recruitment of subjects into the study and shipment of Study Drug. The Investigator's Brochure must be submitted to the IEC/IRB for acknowledgement.

The Investigator must submit to and, where necessary, obtain approval from the IEC/IRB, for all subsequent protocol amendments and changes to the informed consent document. The Investigator should notify the IEC/IRB of deviations from the protocol in accordance with ICH GCP Section 4.5.2. The Investigator should also notify the IEC/IRB of SAEs occurring at the Study Center and other AE reports received from the Sponsor or designee, in accordance with local procedures.

The Investigator will be responsible for obtaining annual IEC/IRB approval/renewal throughout the duration of the study. Copies of the Investigator's reports, all IEC/IRB submissions and the IEC/IRB continuance of approval must be sent to the Sponsor or designee.

#### 11.4 Subject Confidentiality

The Investigator must ensure that the subject's confidentiality is maintained. On the case report forms or other documents submitted to the Sponsor or designee, subjects should be identified by initials (if permitted by local law) and a subject identification number only. Documents that are not for submission to the Sponsor or designee (e.g., signed informed consent forms) should be kept in strict confidence by the Investigator.

In compliance with Federal and local regulations/ICH GCP Guidelines, it is required that the Investigator and institution permit authorized representatives of the company, of the regulatory agency(s), and the IEC/IRB direct access to review the subject's original medical records for verification of study-related procedures and data. Direct access includes examining, analyzing, verifying, and reproducing any records and reports that are important to the evaluation of the study. The Investigator is obligated to inform and obtain the consent of the subject to permit named representatives to have access to his/her study-related records without violating the confidentiality of the subject.

#### 12. ADMINISTRATIVE AND LEGAL OBLIGATIONS

#### **12.1 Protocol Amendments**

Protocol amendments must be made only with the prior approval of the Sponsor or designee. Agreement from the Investigator must be obtained for all protocol amendments and amendments to the informed consent document. The regulatory authority and IEC/IRB must be informed of all amendments and give approval for any amendments likely to affect the safety of the subjects or the conduct of the trial. The Investigator **must** send a copy of the approval letter from the IEC/IRB to the Sponsor or designee.

#### 12.2 Study Termination

The Sponsor or designee reserves the right to terminate the study. The Investigator reserves the right to terminate their participation in the study, according to the terms of the site contract. The Investigator/Sponsor or designee should notify the IEC/IRB in writing of the trial's completion or early termination and send a copy of the notification to the Sponsor or designee.

#### 12.3 Study Documentation and Storage

An electronic case report form (eCRF) utilizing an Electronic Data Capture (EDC) application will be used for this study.

The Investigator should ensure that all appropriately qualified persons to whom he/she has delegated trial duties are recorded on a Sponsor-approved Delegation of Site Responsibilities Form.

Source documents are original documents, data, and records from which the subject's case report form data are obtained. These include but are not limited to hospital records, clinical and office charts, laboratory and pharmacy records, diaries, imaging, and correspondence. Case report form entries may be considered source data if the case report form is the site of the original recording (i.e., there is no other written or electronic record of data).

The Investigator and Study Center staff are responsible for maintaining a comprehensive and centralized filing system of all study-related (essential) documentation in accordance with Section 8 of the ICH Guidelines (E6), suitable for inspection at any time by representatives from the Sponsor or designee and/or applicable regulatory authorities. Elements should include:

- Subject files containing completed case report forms, informed consents, and supporting copies of source documentation
- Study files containing the protocol with all amendments, Investigator's Brochure, copies of prestudy documentation and all correspondence to and from the IEC/IRB and the Sponsor or designee
- If drug supplies are maintained at the Study Center, proof of receipt, Study Drug Product Accountability Record, Return of Study Drug Product for Destruction, final Study Drug product reconciliation, and all drug-related correspondence

In addition, all original source documents supporting entries in the case report forms must be maintained and be readily available.

No study document should be destroyed without prior written agreement between the Sponsor or designee and the Investigator. Should the Investigator wish to assign the study records to another party or move them to another location, he/she must notify the Sponsor or designee.

## 12.4 Study Monitoring

The Sponsor representative and regulatory authority inspectors are responsible for contacting and visiting the Investigator for the purpose of inspecting the facilities and, upon request, inspecting the various records of the trial (e.g., case report forms and other pertinent data) provided that subject confidentiality is respected.

The Sponsor monitor or designee is responsible for inspecting the case report forms at regular intervals throughout the study to verify adherence to the protocol; completeness, accuracy, and consistency of the data; and adherence to local regulations on the conduct of clinical research. The monitor should have access to subject medical records and other study-related records needed to verify the entries on the case report forms.

The Investigator agrees to cooperate with the monitor to ensure that any problems detected in the course of these monitoring visits, including delays in completing case report forms, are resolved.

In accordance with ICH GCP and the Sponsor's audit plans, this study may be selected for audit by representatives from the Sponsor's Clinical Quality Assurance Department (or designees). Inspection of Study Center facilities (e.g., pharmacy, drug storage areas, laboratories) and review of study-related records will occur to evaluate the trial conduct and compliance with the protocol, ICH GCP, and applicable regulatory requirements.

To ensure the quality of clinical data a clinical data management review will be performed on subject data received by the Sponsor or designee. During this review, subject data will be checked for consistency, omissions, and any apparent discrepancies. In addition, the data will be reviewed for adherence to the protocol and GCP. To resolve any questions arising from the clinical data management review process, data queries and/or Study Center notifications will be sent to the Study Center for completion and return to Sponsor or designee.

The Principal Investigator will sign and date the indicated places on the case report form. These signatures will indicate that the Principal Investigator inspected or reviewed the data on the case report form, the data queries, and the Study Center notifications, and agrees with the content.

#### 12.5 Language

Case report forms must be completed in English. Whenever possible, the trade name rather than the generic name for concomitant medications should be recorded and if possible, in English. Generic names are acceptable if the trade name is unknown. Combination medications should be recorded using their trade name in English if possible.

All written information and other material to be used by subjects and investigative staff must use vocabulary and language that are clearly understood.

#### **12.6** Compensation for Injury

The Sponsor maintains appropriate insurance coverage for clinical trials and will follow applicable local compensation laws. Subjects will be treated and/or compensated for any study-related illness/injury in accordance with the information provided in the Compensation for Injury section of the Informed Consent document.

# 14. **APPENDICES**

# **Appendix A Schedule of Procedures**

#### ISIS 703802-CS5

CONFIDENTIAL

Amendment 1 16 February 2018

Protocol

# Appendix A Schedule of Procedures

	Scree	ning				Treat	ment Deries	1			Falls		riad
	Run-in #	Qual †				Treatr	ment Period	1			Folic	ow-up Pe	rioa
Study Week	-6 to -1	-1 to 0	1	5	9	13	17	21	25	27/ET	4*	8*	13*
Study Day	-42 to -1	-7 to -1	1	29	57	85	113	141	169	183	*Weeks from the end of treatment period o		
Visit and Testing Window +/- Days	0	0	0	2	2	2	3	3	3	0	3	3	3
Informed Consent	Х												
Outpatient Visit	Х	Х	Х	Х	Х	Х	Х	Х	Х	Х	Х	Х	Х
Inclusion/Exclusion Criteria	Х	Х	Х										
Medical History	Х												
Genetic Testing p	Х												
Vital Signs	Х		Х	Х	Х	Х	Х	Х	Х	Х	Х	Х	Х
Physical Examination a	Х		Х	Х		Х				Х	Х		Х
Body Weight and Height b	Х	Х	Х	Х	Х	Х	Х	Х	Х	Х	Х	Х	Х
Waist and hip circumference	Х									Х			
DEXA Scan	Xď					Х				Х			
12- lead ECG (triplicate)	Х		Х	Х		Х		Х		Х	Х	Х	Х
Ultrasound	Х												
Mixed Meal Test c		Х				Х				Х			
MRI	Xď	-				Х				Х			
24-Hour Urine for Creatinine Clearance and Protein q		Х											
Extended Urinalysis e	Х		EV	ERY 14 DA	YS (+/- 2 d	ays) e, f	Х	Х	Х	Х	Х	Х	Х
Serum Creatinine and Cys-C i, j, k	Х		EV	ERY 14 DA	YS (+/- 2 d	ays) f, i	Х	Х	Х	Х	Х	Х	Х
Chemistry Panel j, k	Х		E١	/ERY 14 D/	4YS (+/- 2 c	days) f	Х	Х	Х	Х	Х	Х	Х

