# 3.4.1 Screening/Qualification

Subject eligibility for the study will be determined within 42 days/6 weeks prior to study entry. Potential subjects will report to the Study Center for screening assessments at specified intervals within the 6-week screening period as detailed in the Schedule of Procedures in Appendix A. As part of the screening period, subjects will have a 4-week diet stabilization/run-in period followed by a up to 2-week qualification period. Subjects on stable diet known to the investigator and followed at the site may go from Screening to qualification without a 4-week diet run-in. At the qualification visit TGs will be measured. A baseline DEXA scan and MRI will be obtained to assess liver fat content once all other eligibility has been confirmed. MRI results must be available prior to registration and administration of the first dose of study drug.

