#### 6.1.1 Screening/Qualification

Written informed consent for the study will be obtained prior to the performance of any study-related procedures including screening procedures. A 6-week period is provided for completing screening assessments and determining subject eligibility for the study. During the screening period, subject will be advised to maintain diet and exercise routines, and remain on a stable regimen of diabetes and lipid medications (if they are already taking any).

Subjects will undergo a medical history and physical examination including vital signs, 12-lead ECG, and have blood and urine samples taken for clinical laboratory testing. Subjects will be screened for HIV, hepatitis B, and hepatitis C. Safety labs may be re-tested for determination of subject eligibility after consultation with the Sponsor Medical Monitor.

As part of the screening period, subjects not already on a stable diet will have 4 weeks of diet run-in, followed by a qualification visit, during which final eligibility assessments will be performed. Subjects on stable diet known to the investigator and followed at the site may go from Screening to qualification without a 4-week diet run-in. At the qualification visit TGs will be measured. MRI and DEXA scan will be obtained during screening once all other eligibility criteria are met to assess liver fat content. MRI results must be available prior to registration and administration of the first dose of study drug.

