#### 10.1.2 Secondary Endpoints

- Change from Baseline in AUC plasma glucose, serum insulin, serum C-peptide, free fatty acid, serum ghrelin, GIP, GLP-1, and PYY and incretin hormones in response to a mixed meal test (MMT)
- Change from Baseline in lipids and lipoproteins including high-density lipoprotein cholesterol (HDL-C), low-density lipoprotein cholesterol (LDL-C), total cholesterol (TC), very low-density lipoprotein cholesterol (VLDL-C), non-HDL-C, apolipoprotein B (apoB), apolipoprotein B-48 (apoB-48), apolipoprotein B-100 (apoB-100), apolipoprotein A-1 (apoA-1), apolipoprotein C-III (apoC-III :total, chylomicron, VLDL, LDL and HDL), Lipoprotein a [Lp(a)], free fatty acids (FFA), and glycerol levels, lipoprotein particle size/number
- Change from Baseline in glycosylated hemoglobin (HbA1c)
- Change from Baseline in homeostasis model assessment-estimated insulin resistance (HOMA-IR)
- Change from Baseline in adiponectin and leptin
- Change from Baseline in hepatic fat fraction (as assessed by magnetic resonance imaging [MRI])
- Changes from Baseline in body fat distribution for various areas in the body as measured by skinfold thickness and DEXA; VAT and SAT as measured by MRI; body weight, waist circumference and waist/hip ratio
- Change from Baseline in quality of life and pain score

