# **10.4 Definition of Baseline**

For fasting lipid measurements, the Baseline is defined as the average of Day 1 pre-dose assessment and the last measurement prior to Day 1.

For other measurements, Baseline will be the last non-missing assessment prior to the first dose of Study Drug.

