# Subjects on stable diet known to the investigator and followed at the site may go from Screening to qualification without the diet run-in period.

† Qual =Qualification

ISIS 703802-CS5

All procedures and study samples are to be done pre-dose at respective visits, unless specified

- a Full physical exam will be performed at the screening visit and an abbreviated physical exam will be performed during treatment and follow-up periods.
- b Height only required at Screening
- c Mixed Meal Test-refer to Appendix E for further details
- d MRI and DEXA scan will only be performed during Screening after all other eligibility criteria are met. MRI should be performed 10 days (+/- 2 days) prior to anticipated Day 1 date to allow time for result reporting and analysis. DEXA scan should be performed as close to anticipated Day 1 date as possible.
- e All tests listed in Appendix B under Extended Urinalysis should be performed, including routine urinalysis, urine microscopy, UACR and UPCR.
- f Assessments and procedures to be conducted by either a home healthcare service or the Study Center. Subject Study Center visits must be no more than 4 weeks apart during the treatment period.
- g Urine samples for renal biomarkers will be collected. Sample analysis will be conducted in accordance with Safety Monitoring for Renal Function (Section 8.5.2).
- h During follow-up period, hematology sampling for platelet values are taken every 14 days (+/- 2 days) for 6 weeks after last dose of Study Drug, then at Week 8 and Week 13 Follow-up visits.
- i Serum Creatinine and Cys-C will be collected as a part of chemistry panel at visits when chemistry panel is performed, or as stand-alone samples at time points when a chemistry panel is not performed.
- j Blood samples to be collected after an overnight fast of at least 10 hours and preferably not more than 12 hours, unless tests are repeated for safety reasons.
- k If the platelet value, serum creatinine or liver enzyme tests are uninterpretable (e.g., due to clumping, hemolysis or quantity not sufficient) a repeat blood specimen should be re-drawn as soon as possible (ideally within 7 days). All platelet count results will be reviewed promptly (within 48 hours of receipt) by the Investigator as per Section 6.2.1. Any case of a platelet count ≤ 50,000/mm^3 should be reported in an expedited fashion to the Sponsor.
- Refer to Appendix C for PK Sampling schedule.

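### Waist and hip circumference has no scheduled measurement at Qualification or Day 1, so its baseline is not guaranteed to follow the diet run-in

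*Combined protocol and SAP*

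**What the plan says.** Section 10.1.2 lists change from Baseline in body fat distribution as a secondary endpoint, with these measures: "skinfold thickness and DEXA; VAT and SAT as measured by MRI; body weight, waist circumference and waist/hip ratio". Section 10.6.3 includes fat distribution among the changes to be summarized at Week 27.

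In the Amendment 1 schedule (Appendix A), the row "Waist and hip circumference" has two marks. One is in the first Screening column, headed Run-in and covering Day -42 to -1. The other is at Week 27/ET. Qualification and Day 1 have no mark. The pre-amendment schedule has the same row, and none of the clarification letters changes it.

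Section 10.4 sets the baseline rule: "For other measurements, Baseline will be the last non-missing assessment prior to the first dose of Study Drug".

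On the run-in, Section 3.4.1 says "subjects will have a 4-week diet stabilization/run-in period" and then exempts subjects on a known stable diet. Section 6.1.1 makes the condition explicit: "subjects not already on a stable diet will have 4 weeks of diet run-in, followed by a qualification visit". The footnote to Appendix A repeats the exemption: "Subjects on stable diet known to the investigator and followed at the site may go from Screening to qualification without the diet run-in period".

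**The concern.** The waist/hip baseline is whatever the single Screening-column value happens to be. If it is taken at the Screening visit and the subject then spends four weeks stabilizing diet, any waist change over that time falls inside the change from Baseline. There is one treatment group and no comparator, so that part cannot be subtracted or estimated.

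The other body-fat measures are handled differently. Weight is repeated at Qualification and Day 1. Skinfold starts at Day 1 pre-dose, under the first clarification letter. MRI and DEXA sit in the Screening block, but footnote d of Appendix A places MRI about 10 days before Day 1 and DEXA near Day 1. The waist/hip row carries no such footnote. A waist change could therefore cover a longer period, with a different diet history, than the weight and skinfold changes reported beside it.

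**Working it through.** The plan gives no figure to reproduce on this point: there is no power calculation and the analysis is descriptive. The check reads the schedule against the baseline rule and then counts days.

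**Inputs.** Only pre-dose waist/hip mark: Day -42 to -1 (Appendix A). Post-treatment mark: Day 183 (Appendix A). Run-in: 4 weeks, followed by up to 2 weeks of qualification (Section 3.4.1). Baseline: last non-missing pre-dose value (Section 10.4). Sample size: about 3, possibly 6 (Section 3.3).

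**Which value becomes the baseline.** With one scheduled pre-dose assessment, the last pre-dose value is that assessment. The rule cannot produce a later one.

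**What the change contains.** Write W for waist. Then

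W(Day 183) − W(Screening) = [W(Day 1) − W(Screening)] + [W(Day 183) − W(Day 1)].

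The first bracket is pre-drug. It is exactly the difference between a Screening-based and a Day 1-based change. The same split holds for waist/hip ratio.

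**Period covered.** There is no Day 0, so Day -d lies d days before Day 1, and Day 1 to Day 183 is 183 − 1 = 182 days.

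| Waist/hip measured on | Pre-dose days | Total days | Pre-dose share |
|---|---|---|---|
| Day -42 | 42 | 42 + 182 = 224 | 42/224 = 18.8% |
| Day -10 | 10 | 10 + 182 = 192 | 10/192 = 5.2% |
| Day -1 | 1 | 1 + 182 = 183 | 1/183 = 0.5% |
| Day 1 (not scheduled) | 0 | 182 | 0% |

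Of the 42 days in the first row, the run-in accounts for 4 × 7 = 28. The other 2 × 7 = 14 are qualification, so 42 days is the longest calendar gap and not a documented period of diet change.

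**Effect on the mean.** The documents give no run-in waist change, so one must be assumed. If k of n subjects are measured before the run-in and then do it, and each changes by r, the mean shifts by (k/n) × r.

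- r = 0: no shift, whatever k is.
- r = -2 cm, n = 3: k = 1, 2, 3 gives -0.67, -1.33, -2.00 cm.
- r = -2 cm, n = 6: k = 1, 3, 6 gives -0.33, -1.00, -2.00 cm.
- n = 3, k = 1: r = -1 or -3 cm gives -0.33 or -1.00 cm.

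A positive r would shift the mean the other way.

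**The case against.** A reader might infer that waist and hip are measured before the run-in, so that the endpoint credits a diet effect to the drug. The documents do not support that as a statement of fact, for three reasons.

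- **Timing.** The column holding the mark runs to Day -1, and DEXA, marked in the same column, is done near Day 1. Measurement at the Screening visit is the more natural reading, because waist/hip lacks the footnote that moves DEXA and MRI late, but it is not written.
- **Who is affected.** The run-in is conditional. With about three subjects planned at one center, few or none may do it.
- **Diet effect.** None is shown. Subjects are advised during Screening to keep up their diet and exercise routines, and the study diet is moderate in composition with no stated calorie restriction or weight-loss aim. Zero change is plausible.

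The consequence is also limited. Analysis is descriptive, the other body-fat measures have later baselines, and weight at Screening, Qualification and Day 1 would partly reveal a shift in body size during the run-in, though not a waist change directly.

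All of this stands, and it narrows the point. It does not supply a post-run-in waist/hip value: where the plan wanted a late baseline for a neighboring measure, it scheduled or footnoted one.

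**Conclusion.** The gap is real and minor. Waist circumference and waist/hip ratio lack a guaranteed post-run-in baseline. For a subject measured at the Screening visit who then does the run-in, the change can include a pre-drug component of unknown size and direction, over up to 224 days against 182 for weight and skinfold. For subjects who skip the run-in, or are measured late in Screening, no run-in effect enters. The centimeter shifts shown rest wholly on assumed run-in changes and illustrate scale only.

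The primary endpoint is not affected, because the fasting lipid baseline averages the Day 1 value and the last one before it.

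**What to change.** Add waist and hip circumference at Day 1 pre-dose to Appendix A, and keep the Screening value as descriptive. Section 10.4 needs no change: its rule would select the Day 1 value, and the change would cover 182 days with no run-in days inside it.

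The cost is a few minutes of staff time at a visit that already includes a physical examination and weight. There is a precedent: the first clarification letter set skinfold at Day 1 pre-dose to bring the schedule into line with this same endpoint.

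A Day 1 baseline would not remove diet effects that continue after Day 1; without a control group these remain mixed with any drug effect.
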